The 2006 introduction of varenicline, an $\alpha_4\beta_2$ nicotinic acetylcholine receptor partial agonist, represented an enormous breakthrough in adult smoking cessation pharmacotherapy. In addition to its superior efficacy in comparison with placebo (end-of-treatment ORs 3.9-5.9), varenicline was superior in head-to-head trials with the previously established first-line pharmacotherapies: bupropion SR (OR 2.2) and nicotine patch (OR 1.7) (21-25). Some might argue that varenicline would never provide comparable outcomes for adolescent smokers. However, while overall abstinence rates might be lower among adolescent smokers, the effect size

Pro00014398

should be comparable, as we have no reason to believe the mechanism by which varenicline works differs by age group (see below). Thus, given its striking efficacy in adults, varenicline is a strong candidate for evaluation in adolescent smokers. This critical evidence gap needs to be filled.

Only two small pilot feasibility studies of varenicline have been conducted among adolescents. The first was a 2-week pharmacokinetic study (26). Adolescent smokers (ages 12-16, $n=72$) were randomized to receive "high-dose" varenicline (titration to 1 mg twice daily for those >55 kg and to 0.5 mg twice daily for those ≤ 55 kg), "low-dose" varenicline (titrated to 0.5 mg twice daily for those >55 kg and to 0.5 mg once daily for those ≤ 55 kg), or placebo. Results indicated that pharmacokinetics were similar to adults for those >55 kg, and that the body weight exposure effect for those ≤ 55 kg was adequately offset by the reduced dose. Adverse events occurred in more participants in the varenicline groups (64% "high-dose", 73% "low-dose") versus placebo (13%), with nausea, headache, vomiting, and dizziness being most common. Two participants reported abnormal dreams and one had a brief, mild episode of anger. However, there were no serious adverse events or discontinuations due to adverse events in any group. Almost all adverse events were considered mild, and none were more frequent in the "high-dose" versus "low-dose" groups. Though participants were not instructed to reduce or quit smoking, there were moderate reductions in smoking over the 2-week trial (74% cigs/day reduction in "high dose," 52% in "low dose," and 40% in placebo participants).

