The second step towards a sample size analysis is to estimate the effect of varenicline within adolescent smokers. The only existing adolescent varenicline abstinence data come from our recent pilot trial, in which 26.7% of participants achieved cotinine-confirmed 7-day point prevalence abstinence (27). This results in an anticipated effect size (odds ratio) of 5.5. We recognize that this estimate is based on a small sample size ($n=15$ in the pilot trial varenicline group). However, we do not believe the absolute end of treatment 7-day point prevalence abstinence rates from adult varenicline studies (ranging from 50 to 60%) would be appropriate for sample size estimation in this case, as absolute adolescent abstinence rates (see **Table 1**) are consistently lower than those in adult studies (23,24,81). We do, however, believe that varenicline effect sizes may be comparable across adult and adolescent trials. By this measure, our estimates converge. For example, end of treatment abstinence odds ratios in adults were as follows: 3.8 (23), 4.1 (24), and 9.1 (82). Thus, the sample size estimation is based on anticipated abstinence rates of 6.25% (placebo) and 26.7% (varenicline), for an odds ratio of 5.5. With a type 1 error rate of 5% ($\alpha = 0.05$) and power ($1 - \beta$) of 80%, this would require 51 participants per group using a two-sided Pearson's Chi Square test statistic. However, we still wish to aim even more conservatively, recognizing that (a) this effect size may be an overestimate since the varenicline abstinence rate came from a small sample pilot study, and (b) we must account for attrition for the intent-to-treat analysis. In light of the range of odds ratios in prior adult varenicline studies, we have conservatively targeted detection of an odds ratio of 4.0 for power analysis. Original plans were that we will enroll and randomize **83 participants per group**, for a **total sample size of 166**. This will allow us to detect an odds ratio of 4.0 over the anticipated placebo rate of 6.25%, which would correspond to a varenicline abstinence rate of 21.1%. Due to the higher than expected retention losses within our target population of adolescents and following the current ratio of successfully consented to randomized participants, we estimate that 240 participants will need to be enrolled (consented) to meet our sample size needs.

Efficacy: Primary Analysis

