Categorical clinical and demographic variables will be assessed by chi-square tests of independence, while continuous variables will be assessed using Student's *t*-test. The effect of varenicline versus placebo on abstinence at end of treatment will be examined using logistic regression. Models will be computed both unadjusted and adjusted for significant covariates found in the descriptive analysis. For these efficacy analyses, 7-day point prevalence abstinence will be defined as having no cigarettes (or other tobacco/nicotine products) for 7 days, confirmed by urine cotinine level ≤ 50 ng/mL. All randomized participants will be included in the analyses (intent-to-treat approach), and participants will be considered non-abstinent at any missed visit.

Safety: Primary Analysis

Similar to adult varenicline phase III studies (23,24), we define any treatment-emergent adverse event any adverse event occurring between treatment initiation and one week following treatment conclusion. Non-inferiority analysis will be utilized to compare adverse event rates between varenicline and placebo groups (84). With a type 1 error rate of 5% ($\alpha = 0.05$) and power ($1 - \beta$) of 80%, the proposed total sample size of 166 and an estimated placebo rate of treatment-emergent adverse events of 75% (23) will afford a non-inferiority margin (NIM) of 16.7% for the varenicline adverse event rate. We considered incorporating a larger sample

Pro00014398

size that would afford a smaller NIM. However, even to detect a 12.5% NIM, a total sample size of 376 participants would be necessary. That sample size would not be feasible within the proposed funding period.

Smoking-Related Outcomes: Secondary Analysis

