1.3.1 Adverse events related to study medication

The varenicline package insert (http://www.pfizer.com/files/products/uspi_chantix.pdf) details adverse events associated with the medication. Specifically, it reports that “the most common adverse reactions (>5% and twice the rate seen in placebo-treated patients) were nausea, abnormal (e.g., vivid, unusual, or strange) dreams, constipation, flatulence, and vomiting.”

Meta-analyses of the four main adverse events in varenicline versus placebo groups in adult trials yielded relative risks (RRs) of 3.21 (95% CI 2.71, 3.80) for nausea, 1.50 (95% CI 1.26, 1.79) for insomnia, 2.79 (95% CI 2.09, 3.72) for abnormal dreams, and 1.20 (95% CI 1.00, 1.45) for headache (85). Similarly, adverse events in our adolescent pilot cessation trial included insomnia (4/15 participants) nausea (3/15 participants), and headache (3/15 participants) (27). No other adverse events were reported by more than one participant (including abnormal dreams – 1/15 participants). In a 2-week adolescent varenicline pharmacokinetic study, the most common adverse events were nausea, headache, vomiting, and dizziness (26).

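### The 80% power quoted for the primary safety non-inferiority test holds only if both arms have the same adverse-event rate and the test is one-sided at 0.05; neither condition is stated, and the paragraph's two margins imply different alphas

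*Combined protocol and SAP*

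**What the plan says.** Section C3f, under the primary safety analysis, compares the two arms by non-inferiority on treatment-emergent adverse events. An event counts if it is "any adverse event occurring between treatment initiation and one week following treatment conclusion". For alpha 0.05, 80% power and 166 participants, the section states that "an estimated placebo rate of treatment-emergent adverse events of 75% (23) will afford a non-inferiority margin (NIM) of 16.7" percent. It adds that "even to detect a 12.5% NIM, a total sample size of 376 participants would be necessary", which it calls infeasible within the funding period. The sample-size section gives the split as "83 participants per group, for a total sample size of 166".

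The paragraph gives no expected varenicline event rate and does not say whether alpha is one-sided or two-sided. Elsewhere in C3f, sidedness is given only for other tests: two-sided for the efficacy chi-square calculation, and one-sided for the depression/anxiety and suicidality t-tests.

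Other sections report event rates on varenicline:

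- Section A, on the two-week adolescent pharmacokinetic study, says "Adverse events occurred in more participants in the varenicline groups": 64% and 73%, against 13% on placebo.
- The pooled adult table in Section A shows sleep disturbance in 25.1% against 14.5%.
- Human Subjects section 1.3.1 cites adult "relative risks (RRs) of 3.21 (95% CI 2.71, 3.80) for nausea", with 2.79 for abnormal dreams and 1.50 for insomnia.

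**The concern.** The power of a non-inferiority test depends on the true difference between arms as well as on the margin. A single power figure with only a placebo rate beside it carries an unstated assumption about the other arm. If that assumption is a zero difference, any true excess on varenicline uses up part of the margin and power falls.

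The endpoint is any event, mild ones included, so nausea and disturbed sleep count towards it. This is the primary safety outcome and it tests Hypothesis 2. A reader of C3f would take the chance of missing non-inferiority to be 20% for a drug with the tolerability profile the protocol describes. If the chance is materially higher, a failed test could be misread as evidence of inadequate safety when it shows only that the margin was tight for this sample size.

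**Working it through.** **Inputs.** From C3f: 83 per arm, placebo rate 0.75, margin 0.167, alpha 0.05, power 0.80. The margin is read as an absolute difference, a reading supported by the fact that it reproduces. The true excess on varenicline, d, is not in the documents and is varied as an assumption.

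**Reproducing the 16.7% margin.** With true rates of 75% in both arms, SE = √(2 × 0.75 × 0.25 / 83) = 0.0672.

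- One-sided 0.05: (1.645 + 0.842) × 0.0672 = 0.167, which matches the plan.
- One-sided 0.025: (1.960 + 0.842) × 0.0672 = 0.188, which does not.

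**Checking the 12.5% margin.** Total N = 2 × [2 × 0.1875 × (z for alpha + z for power)² / 0.125²].

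- One-sided 0.05: 2 × 148.4 = 296.8, or 298 with each arm rounded up.
- One-sided 0.025: 2 × 188.4 = 376.7, which matches the stated 376.

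So the two pairs in the paragraph rest on different alphas.

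**Power with a true excess d.** Power = Φ[(0.167 − d)/SE − z], where SE = √{[0.75 × 0.25 + (0.75 + d)(0.25 − d)] / 83}. For d = 0.05, SE = √[(0.1875 + 0.1600)/83] = 0.0647 and (0.167 − 0.05)/0.0647 = 1.808. Power is then Φ(1.808 − 1.645) = 0.565 at one-sided 0.05 and Φ(1.808 − 1.960) = 0.440 at one-sided 0.025.

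| Assumed true excess (points) | Power, one-sided 0.05 | Power, one-sided 0.025 |
|---|---|---|
| 0 | 79.9% | 70.0% |
| 2 | 71.7% | 60.2% |
| 3 | 66.9% | 54.9% |
| 5 | 56.5% | 44.0% |
| 8 | 39.7% | 28.2% |
| 10 | 28.9% | 19.1% |

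Simulation of the Wald test (400,000 runs) at 0, 5 and 10 points gave 80.2%, 56.8% and 29.3% at one-sided 0.05, and 70.0%, 44.0% and 19.5% at one-sided 0.025, all within 0.5 point of the formula.

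Holding 80% power at a true excess of 5 points with the 16.7-point margin would take 157 per arm at one-sided 0.05, or 200 per arm at one-sided 0.025.

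**Direction of the excess.** The pharmacokinetic study, the sleep-disturbance rates and the adult relative risks for nausea, abnormal dreams and insomnia all point to more events on varenicline. The intervals for those three relative risks (2.71 to 3.80, 2.09 to 3.72 and 1.26 to 1.79) exclude 1.

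**The case against.** Planning a non-inferiority test at zero true difference is a common convention, and the 16.7% figure reproduces. The defect in that figure is an undisclosed assumption, not a miscalculation. The trial is sized on efficacy, C3f reports only the margin this sample affords, and it says openly that a tighter one was out of reach. All of that stands. It does not remove the need to state the assumption when the protocol's own evidence runs against it.

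The objection on size is also sound. The documents give no varenicline any-event rate beside the 75%. Relative risks for single events do not convert into an any-event excess, since a participant with nausea may already be among the 75%. Not every component rises: psychiatric events other than sleep disturbance were 10.7% against 9.7% (RR 1.02), and anxiety symptoms were 4.5% against 5.0%.

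A reader might infer two stronger conclusions that the documents do not support.

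- *That power is essentially nil at the pharmacokinetic study's difference.* That difference is 51 to 60 points (64 − 13 and 73 − 13), and at most 25 points can be added to a 75% base. The study also lasted two weeks, enrolled ages 12 to 16 and had about 15 placebo participants (72 − 57). It supports a direction, not a size.
- *That the trial will probably fail this test.* Power drops below one half only above an excess of about 6 points at one-sided 0.05 (50.9% at +6), or at about 4 points at one-sided 0.025 (49.5% at +4). The documents do not establish an excess of either size.

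**Conclusion.** The point holds as a matter of disclosure and internal consistency. The stated 80% is the power at equal true rates under a one-sided 0.05 test. The cited evidence makes equal rates unlikely in one direction, so power is lower. How much lower depends on an excess the documents do not supply: about 72% at +2 points, 57% at +5 and 29% at +10 at one-sided 0.05. These figures assume a 75% placebo rate, 83 analysed per arm and an unpooled normal-approximation test.

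Separately, and without any assumption about excess, the paragraph's two margin and sample-size pairs cannot both follow from one alpha. If one-sided 0.025 is intended, power at 16.7 points is 70% even with no excess.

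The plan does not say how a failed test would be interpreted. That it would be reported as inadequate tolerability is a risk to guard against, not something the plan states.

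**What to change.** In the primary safety paragraph of C3f:

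1. State one alpha and its sidedness for this test, and recompute both pairs under it. At one-sided 0.05, 166 participants afford 16.7% and a 12.5% margin needs about 298. At one-sided 0.025, 166 afford 18.8% and a 12.5% margin needs about 377 (378 with each arm rounded up). Settle this before any power figures are inserted.
2. State that the power calculation assumes equal true event rates in the two arms.
3. Replace the single 80% with power over a range of assumed true excess at the chosen alpha, using the matching column of the table above.
4. Report the risk difference with its confidence interval as part of the primary safety result, and say that failing to show non-inferiority is not proof of inadequate safety.

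The cost is SAP wording. No visit, dose or sample size changes. The stated safety power becomes less favourable.

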The primary efficacy outcome is cotinine-verified 7-day point prevalence abstinence at the end of treatment (Week 12). The primary safety outcome is frequency of treatment-emergent adverse events.

Sample Size and Power

The proposed study is powered on the primary efficacy hypothesis that varenicline will increase abstinence (cotinine verified 7-day point prevalence abstinence), relative to placebo, at the end of treatment (Week 12). While 30-day point prevalence abstinence or continuous abstinence outcomes are ideal, we do not believe an adequately powered study for either approach is feasible within the proposed funding period. There is considerable precedent for using 7-day point prevalence as primary outcome in adolescent smoking cessation pharmacotherapy trials (see **Table 1**). We have recently published a conversion method to estimate continuous abstinence from point prevalence outcomes with a fair degree of confidence (80), and we will track other abstinence outcomes as secondary measures.

The first step towards a sample size analysis is estimating cotinine-confirmed 7-day point prevalence abstinence at end of placebo treatment. We estimate this to be 6.25%, based on the placebo-only end of treatment group abstinence rate in our prior bupropion SR/contingency management smoking cessation study, which was conducted in a nearly identical population to that of the proposed study (15). This estimate is consistent with placebo group end of treatment outcomes in other adolescent smoking cessation trials (e.g., 5% in Moolchan et al., 2005; 5.6% in Muramoto et al., 2007) (17,19). The slightly higher rate in our trial will result in a conservative estimate of the expected effect size (active – placebo), thereby increasing sample size and ensuring sufficient power for hypothesis testing.

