Secondary outcomes include the following: a) 7-day biologically confirmed point prevalence abstinence at 6 months, b) continuous abstinence, c) time to lapse (first puff), d) time to relapse (first of 3 consecutive days smoking ≥ 1 cigarette), and e) longitudinal efficacy of varenicline. These will be tested via logistic regression to examine a) point prevalence at 6 months and b) continuous abstinence from targeted quit date (Week 1) to both treatment conclusion (Week 12) and final follow-up visit (Week 26), Cox Proportional hazard models (83) to examine c) time to first lapse (first puff, first cigarette), d) time to relapse (first of 3 consecutive days smoking ≥ 1 cigarette), and e) Generalized Estimating Equation (repeated measures) to examine the entire study time course. Repeated measures analysis of variance will be used to assess treatment effects of varenicline on craving (QSU-B), withdrawal (MNWS), and smoking reinforcement (mCEQ) throughout the study. All efficacy analyses (primary and secondary) will be repeated among participants with $\geq 80\%$ medication adherence, per protocol analysis, and completers analysis. Medication adherence (pill counts), nicotine dependence (mFTQ, AUTOS), motivation/readiness to quit (baseline rating), self-efficacy (GSES), perceived social support (MSPSS), and impulsivity (BIS-11) will be explored as possible moderators influencing the effect of varenicline on abstinence.

Safety: Secondary Analysis

Of particular interest will be adverse events leading to medication discontinuation and the occurrence of treatment-related serious adverse events (SAEs) (see Human Subjects Section 4.6). We will specifically compare neuropsychiatric adverse events (Psychiatric Interview) using non-inferiority testing, as well as depression/anxiety (HADS) and suicidality (C-SSRS) ratings using one-sided 2-sample t-tests. Based on adult literature (34,35), we anticipate no serious adverse events, and appropriate stopping plans are in place (see section C3g) for added precaution.

Participant Retention Analysis

Total number of treatment visits attended will be compared using a Student's *t*-test, while the number of days retained will be assessed using Cox Proportional Hazards regression models.

C3g. Clinical Management Issues

Study Termination

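### Continuous abstinence is to be tested by logistic regression with no method named for an empty or near-empty placebo cell, where the usual Wald test breaks down

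*Combined protocol and SAP*

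**What the plan says.** Section C3f, Smoking-Related Outcomes: Secondary Analysis, lists the secondary outcomes and continues: "These will be tested via logistic regression to examine a) point prevalence at 6 months and b) continuous abstinence". The two windows are "continuous abstinence from targeted quit date (Week 1) to both treatment conclusion (Week 12) and final follow-up visit (Week 26"). The same paragraph adds "All efficacy analyses (primary and secondary) will be repeated among participants with" at least 80% medication adherence, and in per-protocol and completer sets.

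Neither this section nor any other says which test supplies the p-value, or what is done when one arm has no events. Section 4.3 mentions only that data can be exported to the common packages.

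Three other statements bear on how many placebo events to expect:

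- **Sample Size and Power** (C3f) sets placebo 7-day point prevalence at Week 12: "We estimate this to be 6.25" per cent. It also says that an adequately powered study of continuous abstinence is not feasible, although it regards that outcome as ideal.
- **Efficacy: Primary Analysis** (C3f) counts a participant as non-abstinent at any missed visit.
- **Retention Strategies** (C3b) reports that 30-60% of participants completed treatment in the earlier large adolescent trials. Sample Size and Power says that retention losses in this trial have been worse than expected, without a figure.

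**The concern.** Continuous abstinence runs from the quit date with no stated grace period. If the missed-visit rule carries over to it, one missed visit could end a participant's abstinence. The placebo count could then be very small, possibly zero.

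With no events in one arm, maximum-likelihood logistic regression has no finite odds ratio. The standard error of the treatment coefficient becomes enormous, and the Wald p-value shown in the usual coefficient table goes to about 1 even when the two arms clearly differ. The analyst would then either report an uninformative result or choose another method after seeing the data. The second course is the kind of unplanned choice that a SAP exists to prevent.

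**Working it through.** **Reproducing the plan's own figures.** Two-sided alpha 0.05, 80% power, pooled variance under the null, no continuity correction:

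n per arm = [1.96·√(2·p̄·(1−p̄)) + 0.8416·√(p₀(1−p₀) + p₁(1−p₁))]² / (p₁−p₀)²

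- 6.25% v 26.7%: (1.028 + 0.424)² / 0.2045² = 50.5, so 51, as stated ("this would require 51 participants per group using a two-sided Pearson's Chi Square test statistic").
- 6.25% v 21.1%: (0.952 + 0.399)² / 0.1485² = 82.8, so 83, as stated.

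The plan's basis for the primary outcome is therefore reproduced. It gives no corresponding figure for continuous abstinence.

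**Inputs for the check.** 83 per arm and the target odds ratio of 4.0 ("This will allow us to detect an odds ratio of 4.0 over the anticipated placebo rate of 6.25" per cent) come from Sample Size and Power. The placebo continuous-abstinence rate is my assumption, shown over a range up to 6.25%. That ceiling applies to Week 12 and holds only if continuous abstinence is confirmed by the same cotinine rule as point prevalence.

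**Chance of a sparse placebo arm.** P(0 events) = (1−p)^83; P(0 to 2) from the binomial distribution.

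| Assumed placebo rate | P(0 of 83) | P(0 to 2 of 83) |
|---|---|---|
| 6.25% (ceiling) | 0.5% | 10% |
| 5% | 1.4% | 21% |
| 3% | 8.0% | 54% |
| 2% | 18.7% | 77% |
| 1% | 43.4% | 95% |

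**What each test returns (two-sided p, 83 per arm).** Firth is the penalised likelihood-ratio test.

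| Placebo v varenicline | Wald | Fisher | Firth |
|---|---|---|---|
| 0 v 6 | 0.999 | 0.028 | 0.012 |
| 0 v 8 | 0.999 | 0.007 | 0.003 |
| 0 v 10 | 0.999 | 0.0015 | 0.0006 |
| 1 v 7 | 0.061 | 0.064 | 0.032 |
| 1 v 8 | 0.043 | 0.034 | 0.017 |
| 2 v 8 | 0.070 | 0.099 | 0.055 |
| 2 v 9 | 0.046 | 0.057 | 0.031 |

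The failure is complete at zero placebo events, moderate at one and small at two.

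**Power by exact binomial enumeration at 83 per arm.** At odds ratio 4.0 the varenicline rate is 4p/(1−p) ÷ [1 + 4p/(1−p)]. For p = 2% this is 0.0816/1.0816 = 7.5%.

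| Placebo | Varenicline | Wald | Firth |
|---|---|---|---|
| 1% | 3.9% (OR 4.0) | 0.6% | 11% |
| 2% | 7.5% (OR 4.0) | 15% | 34% |
| 3% | 11.0% (OR 4.0) | 39% | 52% |
| 6.25% | 21.1% (OR 4.0; the primary outcome) | 80% | 82% |
| 1% | 8% | 16% | 57% |
| 1% | 25% | 57% | over 99% |

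The last row shows a ceiling. Wald cannot reject when the placebo count is zero, so at a 1% placebo rate its power against a varenicline benefit cannot exceed 1 − 0.434 = 56.6%.

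**Type I error.** With equal rates of 1% to 6.25% in both arms, Firth rejects in 0.1% to 4.1% of trials. Its gain in power is not bought with excess false positives.

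**Subset repeats.** A subset's placebo event count for a given outcome cannot exceed the full-set count. An empty placebo cell in the full set therefore recurs in every subset, and one can also arise in a subset when the full set has a few events.

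**The case against.** **The documents do not name a Wald test.** This is correct. They say only logistic regression, and a likelihood-ratio p-value would fit that wording equally well. The concern is that nothing is specified and that the coefficient-table p-value is the usual default. A plain likelihood-ratio test is not a safe replacement either: for 0 v 3 it gives p = 0.040, against 0.245 for Fisher.

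**An analyst would notice.** Probably, since an empty cell and a standard error in the thousands are hard to miss. But the remedy would then be chosen with the data in view.

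**Few placebo events are not established.** A reader might infer from the 6.25% figure that 0 to 2 placebo events are likely. The documents do not support that: the chance is 10% at 6.25% and passes one half only at about 3% or below. Table 1 gives placebo follow-up point prevalence of 5%, 7% and 10% at 26 weeks; its 3% figure is at 12 weeks. Nor does the plan state that continuous abstinence must be cotinine-confirmed, so the ceiling itself is conditional.

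**A larger drug effect does not weaken the test.** A reader might conclude from the p-values near 1 that the stronger the effect, the weaker the planned test. That is wrong. At 1% placebo, Wald power rises from 16% to 41%, 53% and 57% as the varenicline rate goes from 8% to 12%, 16% and 25%. A low placebo rate limits power; it does not reverse it.

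**Other analyses give partial cover, and power is low anyway.** Both points stand. The Cox models for lapse and relapse address closely related questions, and Firth does not bring the outcome to adequate power at odds ratio 4.0. They reduce the importance of the point but give no reason to leave the method open.

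**Conclusion.** The point holds as a gap in specification for a secondary outcome and for the subset repeats. If the placebo arm has no continuous abstainers, the usual logistic output gives no usable odds ratio and a p-value near 1. The chance of this is 8% to 43% at assumed placebo rates of 3% down to 1%, and 0.5% at 6.25%. Firth regression remains usable there and, at odds ratio 4.0, raises power from 15% to 34% at 2% placebo and from 39% to 52% at 3%.

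These figures rest on assumed continuous-abstinence rates, on 83 per arm, and on reading the unspecified test as Wald. They do not show that the trial would report a false null result. A reader might also extend the concern to the primary Week 12 analysis, but at the planned rates the choice of test hardly matters there (80% v 82%). This is a cheap improvement, not a flaw in the main comparison.

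**What to change.** In C3f, Smoking-Related Outcomes: Secondary Analysis, add a sentence to this effect: continuous abstinence to Week 12 and to Week 26, and the adherent, per-protocol and completer repeats of all abstinence outcomes, will be analysed by Firth penalised logistic regression with penalised likelihood-ratio tests and profile-likelihood confidence intervals, and the risk difference will be reported with a score interval.

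The full-set primary analysis at Week 12 can stay as written. The cost is one SAP sentence and a slightly less familiar method. The sentence should be in place before unblinding, so that no method is chosen in response to an empty cell. It does not cure the low power for continuous abstinence that the plan already acknowledges.
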